After obtaining baseline laboratory and clinical values (including an ECG, PSA, hematologic, and renal and hepatic panels), men will receive oral LDE225 800 mg/day or observation daily for 4 weeks ( $\pm 3$  days) prior to prostatectomy. Patients will have a clinical visit and an ECG and laboratory testing will be performed at 2 weeks and then again at 4 weeks, including a 4-week pre-prostatectomy measurement of PSA and a blood sample to determine plasma LDE225 levels by LC-MS/MS. Previous studies using other oral Hedgehog inhibitors indicate that 4 weeks will allow time for steady-state levels of drug in the plasma and for inhibition of *Gli1* expression ([LoRusso et al. 2011](#)).

Men will undergo radical prostatectomy (with bilateral pelvic lymphadenectomy as appropriate), at which point two 250-mg biopsies of prostate tissue will be obtained, frozen and stored for analysis (including *Gli1* expression, genome-wide expression analysis, intra-prostatic LDE225 levels, Ki-67, and cleaved caspase-3) with the remainder of the prostate tissue then being formalin-fixed paraffin-embedded (FFPE) and cross-sectioned for analysis as per our standard institutional procedures.

Relative fold-changes in mRNA expression of *Gli1* will be determined by first normalizing input amounts of the preoperative biopsy and prostatectomy biopsies to the housekeeping gene *HPRT1*. IHC comparisons between diagnostic biopsy specimens and prostatectomy specimens will be made by calculating immunoreactivity scores (staining intensity  $\times$  percentage cell involvement).

Protocol Version 3: October 6, 2015

All men will receive routine post-operative care, and in addition will have ultrasensitive PSA testing at 1 and 2 months post-op followed by standard PSA testing at the 3 month visit.

Study Schema

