## 4.2 Exclusion criteria

Patients must not meet **any** of the following criteria:

1. Patients who have had major surgery within 4 weeks of enrollment.
2. Patients with concurrent uncontrolled medical conditions that may interfere with their participation in the study.
3. Patients unable to take oral drugs (*e.g.* lack of physical integrity of the upper GI tract or known malabsorption syndromes).
4. Patients who have previously been treated with LDE225 or other Hh pathway inhibitors.
5. Patients who have neuromuscular or muscular disorders (*e.g.* inflammatory myopathies, muscular dystrophy, amyotrophic lateral sclerosis and spinal muscular atrophy) or are on concomitant treatment with drugs that are known to cause rhabdomyolysis (such as statins and fibrates), and that cannot be discontinued at least 2 weeks prior to starting LDE225. If it is essential that the patient stays on a statin for hyperlipidemia, only *pravastatin* may be used with extra caution. Patients should not plan to embark on a new strenuous exercise regimen after initiation of study treatment. (NB: Muscular activities, such as strenuous exercise, that can result in significant increases in plasma CK levels should be avoided whilst on LDE225 treatment).
6. Patients who have taken part in an experimental drug study within 4 weeks or 5 half-lives (whichever is longer) of initiating treatment with LDE225.
7. Patients who are receiving other anti-neoplastic therapy (*e.g.* chemotherapy, targeted therapy or radiotherapy) concurrently or within 2 weeks of starting LDE225.
8. Patients taking moderate/strong inhibitors or inducers of CYP3A4/5 or drugs metabolized by CYP2B6 or CYP2C9 that have narrow therapeutic index, and that cannot be discontinued before starting treatment with LDE225. Medications that are strong CYP3A4/5 inhibitors should be discontinued for at least 7 days and strong CYP3A5 inducers for at least 2 weeks prior to starting treatment with LDE225.
9. No concurrent use of statins (except for pravastatin, *if absolutely necessary*)
10. No concurrent warfarin or Coumadin-derivatives
11. Impaired cardiac function or significant heart disease, including any one of the following:
  - Angina pectoris within 3 months
  - Acute myocardial infarction within 3 months
  - QTc  $>450 \text{ msec}$  on the screening ECG
  - A past medical history of clinically significant ECG abnormalities or a family history of prolonged QT-interval syndrome

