Grade 4 Total bilirubin $> 10.0 \times$ ULN	Discontinuation of study drug
AST or ALT	
Grade 1 ( $>$ ULN - 3.0 $\times$ ULN)	Maintain dose level
Grade 2 ( $>$ 3.0 - 5.0 $\times$ ULN)	Maintain dose level
Grade 3 ( $>$ 5.0 - 20.0 $\times$ ULN)	
 
Discontinuation of study drug
 

Grade 4 ( $>$ 20.0 $\times$ ULN)	Discontinuation of study drug

Recommended dose modifications for LDE225**	
Worst toxicity CTCAE grade* (value)	During a cycle of therapy
Cardiac	
Cardiac - prolonged QTc interval ≥ grade 3 (QTc >500 msec or >60 ms from baseline on at least 2 separate ECGs taken within 1 hour)	
First Occurrence:
 
 
• Omit dose
 
• Perform an analysis of serum potassium and magnesium, and if below lower limit of normal, correct with supplements to within normal limits. Concomitant medication usage must be reviewed.
 
• Perform a repeat ECG within one hour of the first QTc >500 ms
 
• If QTc remains > 500 ms, repeat ECG as clinically indicated but at least once a day until the QTc returns to <480 ms.
 
• Once QTc prolongation has resolved, study treatment may be restarted at a reduced dose level
 
 
Second Occurrence:
 
 
• discontinue patient from further study treatment
 

Cardiac, general	
Grade 1 or 2	Maintain dose level
Grade 3	Discontinuation of study drug
Grade 4	Discontinuation of study drug
Other adverse events**	
Grade 1 or 2	Maintain dose level
Grade 3	Discontinuation of study drug
Grade 4	Discontinuation of study drug
All dose modifications should be based on the worst preceding toxicity. Treatment related toxicities are adverse events that are possibly, probably or definitely related to the study drug.	
If the dose-limiting toxicity recurs in a patient following 2 dose reductions, then further therapy with LDE225 will not be continued.	
If a patient requires a dose interruption of > 21 days from the intended day of the next scheduled dose because of an LDE225-related toxicity, then the patient must be discontinued from the study.	
*Common Toxicity Criteria for Adverse Events (CTCAE Version 4.0).	

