#### 5.1.4 Protocol Stopping Rules

The study will be closed if >3 patients experience a delay in surgery by more than 2 weeks due to drug related toxicities. In other words, if 4 or more patients in the experimental arm have their prostatectomy delayed by more than 2 weeks, we will close the study. In addition, the study will close if we observe >3 patients who experience a grade 3 or grade 4 adverse event that is possibly, probably or definitely related to the study drug. In other words, if 4 or more patients in the experimental arm experience a grade 3 or grade 4 drug-related toxicity the study will be closed.

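### Table 5-1 defines a QTc event by either of two limits but orders the repeat ECG, the follow-up ECGs and the return limit for only one of them

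*Combined protocol and SAP*

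**What the plan says.** The left cell of the QTc row in Table 5-1, labelled grade 3 or worse, gives the event as a QTc above 500 ms "or >60 ms from baseline on at least 2 separate ECGs taken within 1 hour". There are two limbs, an absolute value and a change from baseline, and the change limb needs two ECGs.

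The first-occurrence instructions contain five items. Three carry no QTc value: omit the dose, check potassium and magnesium and review concomitant medication, and the restart line, "Once QTc prolongation has resolved, study treatment may be restarted at a reduced dose level". The other two are tied to the absolute limb. One begins "Perform a repeat ECG within one hour of the first QTc" and goes on to name a value above 500 ms. The other applies only while QTc stays above 500 ms, and says "repeat ECG as clinically indicated but at least once a day until the QTc returns to" below 480 ms. A second occurrence ends study treatment, again with no QTc value attached.

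Section 4.2 excludes men with QTc above 450 ms "on the screening ECG". Section 3.1 sets the on-study ECGs: "Patients will have a clinical visit and an ECG and laboratory testing will be performed at 2 weeks and then again at 4 weeks". The schedule in Section 6.1 agrees, with ECGs at screening, Day 14 and the day of prostatectomy (Day 28 ± 3).

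**The concern.** A safety rule that defines an event in two ways should say, for each, how the event is confirmed, how it is followed and when it is over. This row does so only for the absolute limb. A site that follows the instructions literally has no order to take the confirming ECG after a first large rise at or below 500 ms. If the event is confirmed anyway, the site has no ECG schedule and no criterion on which to base the restart that the row permits. At stake is whether a man whom the table itself places at grade 3 or worse is recognised, and on what evidence he goes back on drug. Two sites, or two clinicians at one site, could handle the same tracing differently and both be within the protocol.

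**Working it through.** The plan gives no figure to reproduce; this is a comparison of wording, with simple arithmetic for scope.

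**Inputs.** Event limits 500 ms and a 60 ms rise, repeat trigger 500 ms and return limit 480 ms (Table 5-1, cardiac row). Screening ceiling 450 ms (Section 4.2). ECGs at screening, Day 14 and Day 28 ± 3 (Section 6.1). 11 men per arm (Section 3.1.4). Assumption: the screening ECG is the baseline, since the row does not say which ECG it means.

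**Step 1: the two limbs side by side.**

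| Element of the row | QTc above 500 ms | Rise above 60 ms, QTc at or below 500 ms |
|---|---|---|
| Counts as an event | yes | yes, on two ECGs within 1 hour |
| Line ordering the second ECG | yes | none |
| Dose omission, electrolytes, medication review | yes | yes |
| Line ordering follow-up ECGs | daily while it stays above 500 ms | none |
| Return limit | below 480 ms | none |
| Restart at a reduced level | yes | yes, once resolved, which is undefined |
| Second occurrence ends treatment | yes | yes |

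**Step 2: which readings fall in the right-hand column.** With baseline b, these satisfy b + 60 < QTc ≤ 500. The interval is non-empty when b < 500 − 60 = 440. In whole milliseconds:

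| Baseline (ms) | Readings meeting only the change limb | Count |
|---|---|---|
| 380 | 441–500 | 60 |
| 400 | 461–500 | 40 |
| 420 | 481–500 | 20 |
| 430 | 491–500 | 10 |
| 439 | 500 | 1 |
| 440–450 | none (first qualifying reading is 501 or more) | 0 |

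Men with a baseline of 440 to 450 ms are fully covered by the 500 ms instructions.

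**Step 3: one man, followed literally.** Baseline 400, Day 14 reading 465. The rise is 465 − 400 = 65 > 60, and 465 ≤ 500. No line orders a repeat. The next scheduled ECG is at Day 28, or Day 25 at the earliest (28 − 3). Suppose instead that a second ECG is taken within the hour and shows 466. The event is met and the dose is omitted, but no line orders another ECG or says what value counts as resolved.

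**Step 4: can the scheduled ECGs fill the gap?** Section 5.1.3 keeps scheduled assessments going while drug is held, and its text ends treatment after an interruption of more than 7 days. From Day 14 that is about Day 21 (14 + 7), before the earliest next ECG at Day 25. A restart inside that limit must therefore rest on an ECG that no line orders. The notes closing Table 5-1 give 21 days instead. That runs to Day 35 (14 + 21), but the Day 28 ECG then falls at surgery, when the course is ending. Under either limit the scheduled ECGs do not supply the missing follow-up.

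**The case against.** The strongest reply is that this is a drafting gap which a competent reader closes. The definition itself asks for two ECGs within an hour, so anyone trying to classify a first 65 ms rise would take a second. Deciding that prolongation has resolved also requires an ECG. Section 5.1.3 continues scheduled assessments and requires follow-up of men who discontinue for an adverse event or abnormal laboratory value. Most of the row's actions apply to both limbs. The table is headed as recommendations, and the expected frequency is low. Finally, the Section 5.1.3 text stops the drug for any grade 3 or 4 toxicity; if that governs, the restart criterion is moot.

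Much of this stands. The change limb is not inoperative: dose omission, the electrolyte and medication checks and the second-occurrence rule all reach it, and once two ECGs exist the event is confirmed by definition. The reply does not supply the missing order for the second ECG, because the instruction that is written points to a narrower trigger. Nor does the restart conflict remove the point. Restart and permanent stop both presuppose that the event has been recognised.

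A reader might also infer that a man on the change limb counts as resolved at onset, because he may already be below 480 ms. That could arise only for baselines below 420 ms (480 − 60) and only if the 480 ms limit is carried across. The text does not carry it across: the limit sits in a sentence conditional on QTc staying above 500 ms, and a man still 66 ms above baseline is not naturally described as resolved. The documents show an undefined criterion, not one met at the outset.

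**Conclusion.** The mismatch is real and confined to one row. For an event met only by the 60 ms rise, the plan orders no confirming ECG, orders no follow-up ECG before the next scheduled one, and gives no resolution criterion before restart. It can arise for any baseline below 440 ms, assuming that the screening ECG is the baseline.

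Its likely frequency is low. Section 1.4.1 reports no treatment-related clinically significant ECG changes in the phase I study of 103 patients, and Section 1.3.3 reports no preclinical QTc signal. Eleven men are assigned to drug, and Day 14 is the only scheduled ECG before the day of surgery, so about 11 scheduled readings can affect dosing, plus any unscheduled ones. The documents give no distribution of baseline QTc, so the share of men exposed to the gap cannot be stated.

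A reader might go on to infer that each unconfirmed event is lost from the closing rule in Section 5.1.4, under which "if 4 or more patients in the experimental arm experience a grade 3 or grade 4 drug-related toxicity the study will be closed". The documents do not show this. Section 7.1.1 treats an abnormal test result as an adverse event only if it produces signs or symptoms or needs therapy, so a symptom-free rise might not be counted even with a confirming ECG.

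The point is worth correcting because it bears on patient safety and is cheap to resolve, not because it threatens the trial's conclusions.

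**What to change.** Reconcile the definition and action cells of the QTc row so that confirmation, follow-up ECGs and the criterion for resolution are each stated for both limbs, and say which ECG is the baseline. The limits themselves are for the sponsor and investigator to set; none is proposed here.

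Do this together with the conflict between this row, which permits restart after a first event of grade 3 or worse, and the Section 5.1.3 text, which discontinues drug for any grade 3 or 4 toxicity. Both changes touch the same lines.

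The cost is wording in one table row, handled as an amendment under Section 9.5, and at most an occasional extra ECG in a man with a rise above 60 ms. Sample size, schedule and analysis are unaffected.

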#### 5.1.4 Protocol Stopping Rules

The study will be closed if >3 patients experience a delay in surgery by more than 2 weeks due to drug related toxicities. In other words, if 4 or more patients in the experimental arm have their prostatectomy delayed by more than 2 weeks, we will close the study. In addition, the study will close if we observe >3 patients who experience a grade 3 or grade 4 adverse event that is possibly, probably or definitely related to the study drug. In other words, if 4 or more patients in the experimental arm experience a grade 3 or grade 4 drug-related toxicity the study will be closed.

### **5.1.5 Permitted concomitant therapy**

Medications required to treat adverse events and manage cancer symptoms, concurrent stable disease (e.g., controlled hypertension) and supportive care agents such as erythropoietin, granulocyte growth factors, or blood transfusion, and pain medications are allowed. The patient needs to notify the investigational site about any new medications he/she takes after the start of the study medication. All medications (other than study drug) and significant non-drug therapies (including physical therapy and blood transfusions) administered after the patient starts treatment with study drug must be listed on the CRF.

### **5.1.6 Permitted concomitant therapy requiring caution and/or action**

LDE225 is an inhibitor of breast cancer resistance protein (BCRP) *in vitro*. Therefore substrates, especially those with a narrow therapeutic range, should be used with caution. BCRP substrates include zidovudine, pantoprazole, cimetidine, sulfasalazine, nitrofurantoin, mitoxantrone, methotrexate, topotecan, imatinib, and irinotecan. *However, the use of statins is generally prohibited during this study (except for pravastatin).*

*In vitro* drug metabolism studies reveal that the metabolism of LDE225 is mediated by CYP3A4 and also a potent inhibitor of CYP2C9 and CYP2B6. Clinical studies have not yet been performed to confirm the potential effect of LDE225 on substrates drugs metabolized by CYP2C9 in patients. Also, it is not known the potential effect of low and moderate CYP3A4 inhibitors and inducers on LDE225 clearance. Therefore, investigators, at their discretion, may administer concomitant medications known to be metabolized by CYP2C9 and CYP2B6, except drugs which have narrow therapeutic index/sensitive substrates for these two isoforms and statins. Caution is advised when LDE225 is co-administered with drugs that are moderate inhibitors or inducers of CYP3A4. Patients receiving such medications must be monitored closely for any potentiation of toxicity or decrease of clinical benefit due to any individual concomitant medications, and may require dose titration or adjustment.

### **5.1.7 Prohibited concomitant therapy**

#### **5.1.7.1 Other investigational therapies**

Other investigational therapies must not be used while the patient is on the study. Anticancer therapy (chemotherapy, immunotherapy, biologic or radiation therapy, and surgery) other than the study treatments must not be given to patients while the patient is on the study medication. If such agents are required for a patient then the patient must be discontinued from the treatment portion of the study.

#### **5.1.7.2 Strong CYP3A inhibitors and inducers**

No clinical studies have been performed to confirm if LDE225 is a sensitive CYP3A4 substrate, *hence concomitant use of strong CYP3A4 inhibitors and inducers is not permitted.*

Patients receiving concomitant medications known to strongly inhibit and/or induce CYP3A4/5 that are deemed medically necessary should be excluded from the study. A partial list of drugs that are inducers, and inhibitors of CYP3A4/5 is included in the [Table below](#). This list of medications has been generated by Novartis Oncology Clinical Pharmacology (OncCP) (DDI database document: last update August 2010) that is compiled by using information listed under “draft guidance for industry, drug interaction studies, CDER 2006”, Indiana University School of Medicine drug interaction tables at

Protocol Version 3: October 6, 2015

<http://medicine.iupui.edu/clinpharm/DDIs/ClinicalTable>, and “drug interaction from University of Washington. Patients should be instructed *not to take grapefruit, St John Wort or Seville (sour) orange juice* while receiving LDE225 treatment throughout the study due to potential CYP3A4/5 inhibition. The other drugs without an asterisk should be carefully used as concomitant therapy.

**Table Medications that are CYP3A4/5 inducers or inhibitors**

Medications	
Inhibitors	HIV antivirals: indinavir, nelfinavir, ritonavir*, saquinavir Antibiotics: azithromycin, ciprofloxacin, chloramphenicol, clarithromycin, erythromycin*, fluconazole&, itraconazole*, ketoconazole*, voriconazole*, telithromycin, posaconazole, norfloxacin Calcium channel blockers: diltiazem&, verapamil& Antidepressants: , fluvoxamine, nefazodone* Miscellaneous: amiodarone, cimetidine, delavirdine, diethyl-dithiocarbamate (chlorzoxazone), interleukin-10*, mifepristone, mibefradil , grape fruit juice&, isoniazid&, aperitant&
Inducers	HIV antivirals: efavirenz, nevirapine Anticonvulsants: barbiturates**, carbamazepine**, oxcarbazepine**, phenytoin**, phenobarbital** Systemic glucocorticoids: dexamethasone&, glucocorticoids, hydrocortisone, prednisolone, prednisone Antibiotics: rifabutin**, rifampicin**,rifapentine** Antidiabetics: pioglitazone, troglitazone Miscellaneous: modafinil, hormone replacement therapy, oral contraceptives, St John's wort**

\*- Known strong inhibitors of CYP3A4 are estimated to cause a  $\geq 5$  fold increase in the AUC values or a  $\geq 80\%$  decrease in clearance of a CYP3A4 substrate;

& - a moderate inhibitor is estimated to cause a 2-5-fold increase in the AUC values or a 50-80% decrease in the clearance of a sensitive substrate when the inhibitor is given at the highest dose.

\*\* - Known strong inducers of CYP3A4/5 (AUC decrease by 50-80%)

#### 5.1.7.3 CYP2B6 and CYP2C9 substrates (narrow therapeutic index)

LDE225 is a potent inhibitor of drugs metabolized by the cytochromes CYP2B6 and CYP2C9 *in vitro*. Because of the potential risk for drug-drug interactions, using concomitant medications known to be metabolized by these enzymes that have low therapeutic index (see [Table below](#)) is not permitted in the study. The other drugs without an asterisk should be carefully used as concomitant therapy.

**Table Drugs metabolized by CYP2B6 and CYP2C9**

CYPs	Drugs metabolized by CYPs
CYP2B6	Bupropion, cyclophosphamide, efavirenz, ifosfamide, methadone
CYP2C9	NSAIDs: diclofenac, ibuprofen, lornoxicam, meloxicam, naproxen, piroxicam, suprofen Oral hypoglycemic agents: tolbutamide, glipizide Angiotensin II blockers: losartan, irbesartan Sulfonylureas: glyburide/glibenclamide, glipizide, glimepiride, tolbutamide

**Miscellaneous:** amitriptyline, celecoxib, fluoxetine, pravastatin, glyburide, nateglinide, phenytoin, rosiglitazone, tamoxifen, torsemide, warfarin\*, quinidine\*

---

\* - narrow therapeutic index: drugs whose exposure-response indicates that increases in their exposure levels by the concomitant use of potent inhibitors may lead to serious safety concerns (e.g. Torsade de Pointes) are not allowed

 - **statins** – If it is essential that the patient takes a statin to control hyperlipidemia [see [Section 5.1.7.5](#)], then only **pravastatin** may be used with extra caution. Pravastatin has the lowest potential of cause rhabdomyolysis compared with other statins (3 cases/ 6 millions of prescription from 1994 to 2002) ([Evans et al. 2002](#)) and the lowest risk for drug-drug interactions with LDE225, as it is primarily transformed in the liver cytosol by sulfonation, not by CYP2C9 or CYP3A4. ([Evans et al. 2002](#))

---

#### 5.1.7.4 Warfarin and coumadin derivatives

Therapeutic doses of warfarin sodium (Coumadin®) or any other coumadin-derivative anticoagulants are not permitted since LDE225 is a competitive inhibitor of CYP2C9 based on the *in vitro* data. An alternative, therapeutic anticoagulation may be accomplished using low-molecular weight heparin.

#### 5.1.7.5 Drugs that may increase risk of rhabdomyolysis

Selected drugs that may increase risk of myopathy and rhabdomyolysis when used concomitantly with LDE225 should be avoided. Such drugs should be discontinued for at least 2 weeks prior to initiation of LDE225 and it must be ensured the plasma CK is within the normal range at baseline. The list compiled below is based on reported association of the individual drugs with muscle toxicity and in addition to the potential risk of clinically relevant PK drug-drug interaction with LDE225 through inhibitory effects on CYP3A4 (enzyme metabolized LDE225) or the inhibitory effect on CYP2C9 by LDE225 of drugs that may induced rhabdomyolysis.

- Azoles: Itraconazole, ketoconazole, fluconazole, voriconazole
- Macrolides: Azithromycin, clarithromycin, erythromycin, telitromycin
- Fibrates: Gemfibrozil, fenofibrate
- HMG CoA reductase inhibitors\* (“statins”): Atovastatin, Fluvastatin, Fluvastatin, Lovastatin, Rosuvastatin and Simvastatin
- Antiretrovirals: Indonavir and ritonavir
- Others: phenobarbital, barbiturates, phenytoin and isoniazid

*\* If it is essential that the patient stays on a statin to control hyperlipidemia [see [Section 5.1.7.5](#)], only pravastatin may be used with extra caution; CK should be monitored weekly during treatment with LDE225.*

